10.2 Adverse Events

All adverse event summaries will be restricted to Treatment Emergent Adverse Events (TEAE), which are defined as those AEs that occurred after dosing and those existing AEs that worsened during the study. Verbatim terms on case report forms will be mapped to preferred terms and system organ classes using the MedDRA dictionary (version 9.1).

Each adverse event summary will be displayed by dose cohort. Summaries that are displayed by system organ class and preferred terms will be ordered by descending order of incidence of system organ class and preferred term within each system organ class. Summaries of the following types will be presented:

- Subject incidence of TEAEs and total number of unique TEAEs by MedDRA system organ class and preferred term;
- Subject incidence of TEAEs by MedDRA system organ class, preferred term, and highest severity. At each level of subject summarization a subject is classified according to the highest severity if the subject reported one or more events. AEs with missing severity will be considered severe for this summary;

- Subject incidence of TEAEs by MedDRA system organ class, preferred term, and closest relationship to study drug (Related/Not Related). At each level of subject summarization a subject is classified according to the closest relationship if the subject reported one or more events. AEs with a missing relationship will be considered related for this summary;
- Subject incidence of serious TEAEs and total number of unique serious TEAEs by MedDRA system organ class and preferred term.

10.3 Clinical Laboratory Evaluation

Before the first dose of medication and at Day 15 (Pre-Dose), Day 16, Day 28, Day 59, Day 91, Day 180 and Day 365 of the study, clinical laboratory evaluations (Hematology, Chemistry, Urinalysis) will be taken. Laboratory parameters will be summarized using descriptive statistics at baseline and at each post baseline time point. Changes from baseline will also be summarized. Baseline is defined as the last non-missing value prior to first dose of study drug.

In addition, shift tables (i.e., low-normal-high at baseline versus low-normal-high at follow-up in a 3-by-3 contingency table) will be provided to assess changes in laboratory values from baseline to most abnormal follow-up result.

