5.3 Exclusion Criteria

To participate in this study a subject may not meet any of the following criteria:

- 1. Subjects who have undergone a revascularization procedure or sympathectomy within 12 weeks prior to study entry that remains patent. A failed revascularization procedure in the previous 4 weeks is acceptable.
- 2. Subjects with grade 3 (hemorrhages, exudates) or grade 4 (papilledema) retinopathy
- 3. Subjects currently receiving immunosuppressive medications, chemotherapy, radiation therapy
- 4. Subject with aorto-iliac occlusion (greater than 75%)
- 5. Subjects that will require amputation within 4 weeks of randomization
- 6. Subjects with any co-morbid conditions likely to interfere with assessment of safety or efficacy or with an estimated life expectancy of less than 6 months
- 7. Subjects with history of drug (defined as illicit drug use) or a history of alcohol abuse (defined as regular or daily consumption of more than 4 alcoholic drinks per day) within the past 3 months

- 8. Subjects with a current history or new screening finding of malignant neoplasm except for basal cell carcinoma of the skin and squamous cell carcinoma of the skin (if excised and no evidence of recurrence)
- 9. Subjects with evidence of active infection (e.g., cellulitis, osteomyelitis) or deep ulceration exposing bone or tendon in the extremity planned for treatment
- 10. Subjects with a clinically significant abnormality in routine hematology, urinalysis, chemistry, liver function or other laboratory tests, including HIV, Hepatitis B (HepBSAg), Cytomegalovirus (CMV), Hepatitis C Virus (HCV), Venereal Disease Research Laboratory test (VDRL), prostate-specific antigen (PSA) and chorio-embryonic antigen (CEA), or signs of malignant neoplasm by radiological imaging tests, including chest radiograph at Screening or Day 1.

Specific laboratory exclusion criteria include the following:

- Hemoglobin less than 9.0 G/dl
- WBC count less than 3,000
- Platelet count less than 75,000
- Fasting glucose greater than 250 mg/dl
- AST and/or ALT greater than 3x upper limit of normal
- 11. Subjects with any other condition that in the opinion of the Investigator might put the subject at risk or interfere with his/her participation
- 12. Subjects unwilling or unable to comply with the protocol or to cooperate fully with the Investigator or site personnel

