8.0 Adverse Events and Serious Adverse Events

8.1 Adverse Event Definition

An AE is the development of an undesirable medical condition or the deterioration of a pre-existing medical condition following or during exposure to a pharmaceutical product, whether or not considered causally related to the product. AEs will be graded according to the National Cancer Institute's Common Terminology for Adverse Events v3.0 criteria.

An undesirable medical condition can be symptoms (e.g., nausea, chest pain), signs (e.g., tachycardia, enlarged liver) or abnormal results of an investigation (e.g., laboratory findings, electrocardiogram).

Therefore, an AE would include the following:

- Any event that is new (i.e., was not seen prior to the start of the study).
- A condition detected or diagnosed after the trial medication administration, even though it may have been present prior to the start of the study.
- A pre-existing intermittent event or condition that recurs with increased intensity and/or frequency after the start of the study.
- A pre- or post-treatment event that results from study participation (i.e., invasive procedures, modification of subject's therapeutic regimen)
- A change in blood pressure or heart rate that results in discontinuation of dosage or that exceeds protocol-specified criteria

An AE does not include the following:

- The disease or disorder being studied, or a sign or symptom of that disease or disorder, unless it is more severe than expected for the subject's condition.
- An overdose of the study medication if the subject is asymptomatic.
- A medical or surgical procedure (e.g., surgery, endoscopy, tooth extraction).
 Depending on the trial design, such a procedure may be the result of an AE or may result in an AE, but is not an AE itself.
- A pre-existing condition or disease that does not worsen following study drug administration.
- Hospitalization for elective surgery for a pre-existing disease or condition that did not worsen or for cosmetic surgery.

In this study an AE can include an undesirable medical condition occurring at any time after screening procedures have been started until the final follow-up visit, even if no study treatment has been administered.

When an adverse event occurs, the Investigator must:

- 1. assess whether or not the test article caused the AE;
- 2. determine the intensity of the AE;
- 3. record the action taken regarding the test article;

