| High | n (%) | n (%) | n (%) | n (%) | n (%) | n (%) | n (%) | n (%) | n (%) | n (%) | n (%) | n (%) | |
| Normal | n (%) | n (%) | n (%) | n (%) | n (%) | n (%) | n (%) | n (%) | n (%) | n (%) | n (%) | n (%) | |
| Low | n (%) | n (%) | n (%) | n (%) | n (%) | n (%) | n (%) | n (%) | n (%) | n (%) | n (%) | n (%) | |
| | | | | | • • | | | | | | | | |

path\t_program.sas date time

Programmer Note If a subject has both a High and Low post dose result, the subject will be assigned a High result for the Most Abnormal Post Dose Result,. Analytes to be shown include Hematocrit, Hemoglobin, RBC, WBC, Platelets, Neutrophils, Lymphocytes, Monocytes, Eosinophils, Basophils, MCV, MCHC, MCH.

^[1] Baseline defined as measurement taken most closely prior to first study drug administration.

^[2] Follow Up defined as most abnormal post dose result.

Viromed Co., Ltd. Page 1 of x Protocol Number: US-06-1-001

T-11- 47 0

| Table 17.2 |
|--------------------------------|
| Chemistry- Shift from Baseline |
| Safety Population |

| Baseline [1] | | | | | | | | | | | | |
|-----------------|-------------------------------|---|---------------------|----------------------------|-----------------------------|---|---|--|--|--|---|--|
| VM202-2 mg (N=) | | | VM | VM202-4 mg (N=) | | | VM202-8 mg (N=) | | | VM202-16 mg (N=) | | |
| High | Normal | Low | High | Normal | Low | High | Normal | Low | High | Normal | Low | |
| | | | | | | | | | | | | |
| n (%) | n (%) | n (%) | n (%) | n (%) | n (%) | n (%) | n (%) | n (%) | n (%) | n (%) | n (%) | |
| | n (%) | | n (%) | n (%) | | n (%) | n (%) | | n (%) | n (%) | n (%) | |
| n (%) | n (%) | n (%) | n (%) | n (%) | n (%) | n (%) | n (%) | n (%) | n (%) | n (%) | n (%) | |
| | | | | | | | | | | | | |
| n (%) | n (%) | n (%) | n (%) | n (%) | n (%) | n (%) | n (%) | n (%) | n (%) | n (%) | n (%) | |
| | n (%) | | n (%) | n (%) | | n (%) | n (%) | | n (%) | n (%) | n (%) | |
| n (%) | n (%) | n (%) | n (%) | n (%) | n (%) | n (%) | n (%) | n (%) | n (%) | n (%) | n (%) | |

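### The supplementary laboratory shift tables use only Low, Normal and High, so they cannot show further worsening in subjects who enter with an abnormal value

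*SAP*

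**What the plan says.** SAP 10.3 plans two kinds of laboratory summary. The first is descriptive statistics of values and of changes from baseline at each time point (Tables 16.1-16.3). The second is described as additional: "shift tables (i.e., low-normal-high at baseline versus low-normal-high at follow-up in a 3-by-3 contingency table) will be provided". For these tables the layouts in SAP Appendix B add "Follow Up defined as most abnormal post dose result" and the programming rule "If a subject has both a High and Low post dose result, the subject will be assigned a High result". Neither the SAP text nor the layouts contain a severity level.

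Protocol 5.3, exclusion 10, bars clinically significant laboratory abnormalities and then lists specific limits, among them "AST and/or ALT greater than 3x upper limit of normal", "Fasting glucose greater than 250 mg/dl", "Hemoglobin less than 9.0 G/dl" and "WBC count less than 3,000", and a platelet count below 75,000.

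Protocol 4.1.1 defines the laboratory primary safety endpoint as change from baseline at named days. Protocol 8.1 says that "AEs will be graded according to the National Cancer Institute's Common Terminology for Adverse Events v3.0 criteria". Protocol 9.3 asks only that laboratory abnormalities be summarized as low and high.

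**The concern.** A shift table is meant to show how far individual subjects moved from where they started. With three categories it can do so only for a subject who starts Normal or who crosses to the opposite side. A subject who starts High and goes much higher, or starts Low and goes much lower, stays in the same cell as a subject whose value never changed.

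The entry criteria make such starting points possible. The AST/ALT limit is itself written as a multiple of ULN, so a baseline between 1 and 3 times ULN is High by definition. This matters because the shift table is the only planned laboratory summary built on each subject's worst post-dose value. Tables 16.1-16.3 work visit by visit and show results and changes in separate columns, without tying a change to the baseline from which it came.

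**Working it through.** The documents give no figure to reproduce on this point. The check applies the SAP's category rule to values that pass the numeric entry limits, and then asks what the other planned outputs would show.

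**Step 1: category rule.** A value above ULN is High, a value below the lower limit of normal (LLN) is Low, and anything else is Normal. For AST/ALT the unit is multiples of ULN, so the boundary is 1 and no reference range has to be assumed. For the other analytes the documents give no reference range, so the ranges below are assumptions.

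| Analyte | Baseline to worst post-dose | Reference limit | Cell |
|---|---|---|---|
| ALT (x ULN) | 1.0 to 1.1 | 1 | Normal to High |
| ALT (x ULN) | 1.1 to 3 | 1 | High to High |
| ALT (x ULN) | 2.9 to 5 | 1 | High to High |
| ALT (x ULN) | 2.9 to 10 | 1 | High to High |
| ALT (x ULN) | 2.9 to 20 | 1 | High to High |
| Hemoglobin (g/dl) | 9.0 to 6.0 or 5.0 | LLN 12 to 13.5, assumed | Low to Low |
| Platelets (thousands) | 75 to 20 | LLN 130 to 150, assumed | Low to Low |
| Fasting glucose (mg/dl) | 250 to 500 | ULN 100 to 110, assumed | High to High |

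The table marks a rise of 0.1 times ULN as a shift but not a rise of 20 - 2.9 = 17.1 times ULN. Each assumed range gives the same cell at both of its ends.

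**Step 2: what Tables 16.1-16.3 would show.** These print N, mean, SD, median, minimum and maximum of the change. Take illustrative ALT changes at one visit, in multiples of ULN.

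- Cohort of 3 with changes -0.1, 0.1 and 17.1: mean = 17.1/3 = 5.70. SD = sqrt[((-5.8)² + (-5.6)² + 11.4²)/2] = sqrt(194.96/2) = 9.87. Median 0.1, minimum -0.1, maximum 17.1. With three subjects, the minimum, median and maximum are the three individual changes.
- Cohort expanded to 6 with changes -0.2, -0.1, 0.0, 0.1, 0.2 and 17.1: mean = 17.1/6 = 2.85, SD 6.98, median 0.05, minimum -0.2, maximum 17.1. The extreme change is still printed.

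A large worsening at a scheduled visit is therefore visible in the analysis of the endpoint.

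**Step 3: where the shift table is not fully backed up.** Protocol 6.2.12 and Table 4-1 call for clinical laboratory tests at unscheduled visits. SAP 10.3 names only scheduled days, so a peak seen at an unscheduled visit may not reach Tables 16.1-16.3. It would be in the listings, and in the adverse event tables if it was reported as an event. The SAP does not say whether unscheduled values count towards the most abnormal result in Tables 17.1-17.3.

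**Step 4: direction.** Under the High-over-Low rule, a subject with both kinds of post-dose result is recorded as High. A subject who starts Low, falls much further and has a single High value would print as Low to High, and the fall would not appear in the table.

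**The case against.** The strongest case against acting is that nothing important is lost. The primary endpoint is change from baseline, and SAP 10.3 analyses it directly. Listings 17-19 allow every baseline and follow-up pair to be read in a study of 12-15 subjects. Protocol 8.3 makes clinically significant worsening of a baseline abnormality an adverse event, and SAP 10.2 tabulates events by highest severity. Exclusion 10 bars clinically significant abnormalities, so passing a numeric limit does not by itself make a subject eligible. The SAP follows Protocol 9.3, and the protocol adopts CTCAE for adverse events rather than for laboratory values. The dose-limiting toxicity definition in Protocol 7.1.9 contains no laboratory criterion, so no written escalation rule uses the shift tables.

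Most of this stands, and it sets the size of the point. It does not make the tables fit for their stated use. The adverse event route depends on the investigator's judgment of clinical significance, and under Protocol 8.5 a known diagnosis, or otherwise signs and symptoms, is recorded in place of the laboratory finding. The adverse event tables are therefore not a systematic display of laboratory worsening. Listings show everything but summarize nothing.

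A reader might infer that worsening is hidden within a primary safety endpoint, or that one affected subject in a cohort of three (33%) would be reported as 0% worsened. The documents support neither reading. The endpoint is not the shift category, and no planned table prints a percentage worsened. Such a subject would appear in the High/High or Low/Low cell: visibly abnormal, but not visibly worse.

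**Conclusion.** The point holds for the supplementary shift tables only. For a subject who enters abnormal, Tables 17.1-17.2 cannot distinguish a stable value from a large deterioration in the same direction. For AST/ALT this follows from the protocol's own limit, provided that High means above ULN. For hemoglobin, WBC, platelets and glucose it also depends on reference ranges that the documents do not give. The subjects affected are those whose baseline abnormality was judged not clinically significant, and the documents do not allow their number to be estimated.

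The consequence is limited. Tables 16.1-16.3, Listings 17-19 and graded adverse events would bring most large changes to light. This is a modest and inexpensive reporting improvement, and it does not threaten the primary safety analysis.

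**What to change.** Keep Tables 17.1-17.3 and supplement 17.1-17.2 with a cross-tabulation of baseline grade against worst post-dose grade for the analytes that can be graded. Use CTCAE v3.0, which the protocol already adopts for adverse events, or prespecified multiples of ULN and LLN. Tabulate the high and low directions separately, so that the High-over-Low rule is not needed there. State that unscheduled post-dose values count towards the worst grade. Keep Low/Normal/High for ungraded analytes.

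As an illustration only, a single cut at the protocol's own 3 times ULN would move ALT from 2.9 to 20 times ULN off the diagonal. It would leave 1.1 to 2.9 on it, so any banding still hides changes within a band and the visit-level change tables remain necessary.

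No new data are required: the values are collected, and Protocol 10.2.2 already requires reference ranges from local laboratories. The cost is an SAP edit, somewhat longer tables and programming of grade limits. Those limits are not listed in either document and would have to be written into the SAP.

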10.4 Physical Examinations

At Screening, a physical examination will be carried out on the following body systems: HEENT, Skin/Dermatologic, Lymph Nodes, Chest/Lungs, Heart/Cardiovascular, Abdomen, Extremities, Neurologic, Stool for Occult Blood, Other. Assessments for each of the body systems will be one of the following: Normal, Abnormal-Not Clinically Significant, Abnormal-Clinically Significant, Not Done. At Day 15 (Pre-Dose), Day 28, Day 59, Day 91, Day 180 and Day 365, changes in any of the body systems will be recorded.

Shift tables will be provided to assess changes in body systems from baseline to each follow up visit.

10.5 Vital Signs

At each visit, vital signs will be collected. Additional vital signs will be collected on the days of dosing (Day 1 and Day 15) at 15, 30 and 60 minutes post dose. Vital signs will be summarized using descriptive statistics at baseline and at each post baseline time point.

Changes from baseline will also be summarized. Baseline is defined as the last non-missing value prior to first dose of study drug.

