Subjects selected for this study will all have critical limb ischemia defined as partial or complete obstruction of a major artery perfusing either the upper or lower extremity that results in pain either at rest or with exertion, numbness, coldness and/or skin ulceration. They may also be a history of prior amputation, dry gangrene or atrophy associated with the above symptoms. Subjects will not be a candidate for either surgical revascularization or angioplasty.

Number of Study Subjects

There will 12-15 subjects selected for participation in this study with 3 subjects treated in each of four (4) study cohorts. There will be an additional 3 patients treated in a cohort if 1/3 subjects experiences a DLT and if the DSMC recommends continuing the trial.

Schedule of Assessments

The schedule of assessments is listed below in Table 4-1.

Table 4-1 Study Procedures Chart	Screen / Baseline		Treatment Period												
		Firs	First Dose Follow-Up Second Dose 2 nd Follow-Up ⁵												
	Day -30 to Day 1	Day 1 pre-dose	Day 1 post-dose	Day 8 (+/- 2days)	Day 15 Pre dose (+/- 3 days)	Day15 Post-dose	Day 16	Day 21 (+/- 3 days)	Day 28 (+/- 3 days)	Day 59 (+/- 7 days)	Day 91 (+/- 7 days)	Day 180 (+/- 10 days)	Day 365 (+/- 10 days)	Unscheduled Visit	Early Termination
Consent Form	X														
Confirm Eligibility		X													
Medical History	X														
Chest X-ray or CT scan of chest ¹	X												X		X
Physical Exam	X				X				X	X	X	X	X	X	X
Vital Signs (HR, BP, Respiratory)	X	X	X	X	X	X	X	X	X	X	X	X	X	X	X
Retinal Fundoscopy	X												X		X
Pregnancy Test	X				X 6										
Photograph and measurement of ulcer	X	X			X				X	X	X	X	X		X
Clinical Lab Tests	X	X			X		X		X	X	X	X	X	X	X
Tumor markers ²	X				X					X		X	X		
Infection tests ³	X									X		X	X		X
Serum HGF		X		X	X			X		X					
anti-HGF antibodies		X			X					X		X		X	X
Blood VM202 DNA		X						X		X^7					
12-lead ECG	X														
High Resolution MRA	X										X	X			X
Hemodynamic Assessment (ABI, TBI,	X	X			X				X	X	X	X	X	X	X
Wave Form)	Λ	Λ			Λ				Λ	Λ	Λ	Λ	Λ	Λ	Λ
Pain VAS	X	X			X				X	X	X	X	X	X	X
Subject Analgesic use	X	X		X	X		X	X	X	X	X	X	X	X	
TcPO ₂	X	X			X				X	X	X	X	X	X	X
Injection site reaction assessment			X	X		X	X	X	X	X					
Mammogram ⁴	X														
Endothelial Progenitor Cell Assay	X		X			X			X	X		X	X	X	X
Concomitant Medications	X	X		X	X		X	X	X	X	X	X	X	X	X
Adverse Events		X	X	X	X	X	X	X	X	X	X	X	X	X	X

CT scan of the chest instead of chest X-ray will be performed if previous tobacco use

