- Review all prior evaluations and confirm that subject meets all entry criteria
- Vital signs
- Digital photography and measurement of ulcer (if present)
- Clinical laboratory tests (chemistry, hematology, and urinalysis)
- Serum HGF
- Anti-HGF antibody level
- VM202 DNA level
- Hemodynamic assessments (ABI, TBI, Wave Form)
- TcPO₂
- Pain VAS
- Analgesic use
- Concomitant medications
- Adverse Events

If the subject meets all eligibility criteria, the following will be performed:

- Obtain study drug from the pharmacy
- Administer study drug in 8 separate injections as described above

After study drug administration, the subject will remain in a comfortable, supine position for observation for at least 60 minutes prior to being discharged. Any adverse reaction occurring during this period will be documented on the CRF.

Following study drug administration, the following evaluations will be performed:

- Vital signs (immediately after study drug administration and at 15, 30, and 60 minutes post-dose)
- Endothelial progenitor cell assay
- Concomitant medications
- Injection site reaction assessment

Adverse events

The subject is instructed to call the Study Coordinator if any of the following occur after discharge from the clinic:

- Hives
- Fever
- Rash
- Difficulty breathing
- Itching
- Worsening of a leg ulcer
- Redness or flushing at the site of the test dose

If any of the above occurs, the subject will be instructed to call the clinic immediately and seek medical attention either at the clinic or to go to the nearest Emergency Room for immediate treatment and evaluation. No further study drug administration will occur until it is determined if this is a DLT or as directed by the treating physician.

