| Abnormal, Clinically Significant | n (%) | n (%) | n (%) | n (%) | n (%) | n (%) | n (%) | n (%) | n (%) | n (%) | n (%) | n (%) | |
| Day 28 | n | | | n | | | n | | | n | | | |
| Normal | n (%) | n (%) | n (%) | n (%) | n (%) | n (%) | n (%) | n (%) | n (%) | n (%) | n (%) | n (%) | |
| Abnormal, Not Clinically Significant | n (%) | n (%) | n (%) | n (%) | n (%) | n (%) | n (%) | n (%) | n (%) | n (%) | n (%) | n (%) | |
| Abnormal, Clinically Significant | n (%) | n (%) | n (%) | n (%) | n (%) | n (%) | n (%) | n (%) | n (%) | n (%) | n (%) | n (%) | |
| Day 59 | n | | | n | | | n | | | n | | | |
| Normal | n (%) | n (%) | n (%) | n (%) | n (%) | n (%) | n (%) | n (%) | n (%) | n (%) | n (%) | n (%) | |
| Abnormal, Not Clinically Significant | n (%) | n (%) | n (%) | n (%) | n (%) | n (%) | n (%) | n (%) | n (%) | n (%) | n (%) | n (%) | |
| Abnormal, Clinically Significant | n (%) | n (%) | n (%) | n (%) | n (%) | n (%) | n (%) | n (%) | n (%) | n (%) | n (%) | n (%) | |
| | | | | | | | | | | | | | |

path\t_program.sas date time

Programmer Note Repeat for all available time points and body systems. Body Systems to be shown include HEENT, Skin/Dermatologic, Lymph Nodes, Chest/Lungs, Heart/Cardiovascular, Abdomen, Extremities, Neurologic, Stool for Occult Blood, Other.

^[1] Abn, Not CS= Abnormal, Not Clinically Significant

^[2] Abn, CS= Abnormal, Clinically Significant

Viromed Co., Ltd. Protocol Number: US-06-1-001

Table 19 Vital Signs Safety Population

| | VM202- 2 | mg (N=) | VM202-4 | mg (N=) | VM202-8 | mg (N=) | VM202-16 mg (N=) | | |
|------------------------------|--------------|--------------|--------------|--------------|--------------|--------------|-------------------|--------------|--|
| Vital Sign | Result | Change [2] | Result | Change [2] | Result | Change [2] | Result | Change [2] | |
| T (D (4) | | | | | | | | | |
| Heart Rate (bpm) | | | | | | | | | |
| Baseline [1] | | | | | | | | | |
| N (GD) | n | | n | | n | | n | | |
| Mean (SD) | xx.x (xx.xx) | | xx.x (xx.xx) | | xx.x (xx.xx) | | xx.x (xx.xx) | | |
| Median | XX.X | | XX.X | | XX.X | | XX.X | | |
| Min, Max | XX, XX | | XX, XX | | XX, XX | | XX, XX | | |
| Day 1 (15 Minutes Post Dose) | | | | | | | | | |
| N | n | n | n | n | n | n | n | n | |
| Mean (SD) | xx.x (xx.xx) | xx.x (xx.xx) | |
| Median | XX.X | XX.X | |
| Min, Max | xx, xx | XX, XX | |
| Day 1 (30 Minutes Post Dose) | | | | | | | | | |
| N | n | n | n | n | n | n | n | n | |

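### Changes after the second dose are all measured from before the first dose, so the SAP plans no within-subject summary of the acute second-dose change

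*SAP*

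**What the plan says.** **Vital signs.** SAP 10.5 plans that "Additional vital signs will be collected on the days of dosing (Day 1 and Day 15) at 15, 30 and 60 minutes post dose" and that "Vital signs will be summarized using descriptive statistics at baseline and at each post baseline time point". It fixes one reference for every change: "Changes from baseline will also be summarized. Baseline is defined as the last non-missing value prior to first dose of study drug". The Table 19 footnote repeats that reference.

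**Labs.** SAP 10.3 schedules hematology, chemistry and urinalysis "Before the first dose of medication and at Day 15 (Pre-Dose), Day 16, Day 28" and at later visits, and defines baseline in the same words. The footnotes to Tables 16.1 to 16.3 agree. In those shells a Day 15 pre-dose row stands directly above the Day 16 row.

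**Collection.** In Protocol Table 4-1 the row "Vital Signs (HR, BP, Respiratory)" is marked both before and after dosing on Day 15. Labs are marked at Day 15 pre-dose and Day 16.

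**Timing of post-dose readings.** Protocol 6.2.2 (Day 1) asks for "Vital signs (immediately after study drug administration and at 15, 30, and 60 minutes post-dose)". Protocol 6.2.4 (Day 15) names the same four times but places them in the list of procedures done before administration. Its post-dose list says only that vital signs are taken. SAP 10.5 names 15, 30 and 60 minutes only. In the Table 19 shell the first row after baseline is "Day 1 (15 Minutes Post Dose)".

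**The concern.** Serial readings around an injection show what happens in the hour after it. On Day 1 the change column does this, because the reference is normally the same-day pre-dose value. On Day 15 the same column takes its reference from about two weeks earlier, so one label carries two meanings in one table. The Day 16 labs, the only scheduled labs within about a day after either dose, have the same problem.

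Safety and tolerability are the primary objective, and the protocol synopsis lists vital signs and signs of acute hypersensitivity among the safety assessments. A fall or rise after the second dose can look smaller or larger in the change column than it was, depending on where the subject stood that day before dosing. With three subjects per cohort, one subject's extreme change is what a reader looks for, and no planned table gives the range of the acute second-dose change.

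**Working it through.** The documents give no figure on this point, so there is nothing to reproduce.

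**1. What the planned column contains.** For each subject:

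(Day 15 post − Day 1 pre) = (Day 15 pre − Day 1 pre) + (Day 15 post − Day 15 pre)

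Only the last term is the acute second-dose change. For labs, read Day 16 for Day 15 post. With the ±3-day window on Day 15, the first term spans 15 − 1 − 3 = 11 to 15 − 1 + 3 = 17 days. It holds ordinary drift and any lasting effect of the first dose. If the true acute change were −10 units and the first term lay between −10 and +10 (both assumed), the column would show −20 to 0.

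**2. What can be recovered from the tables.** One three-subject cohort was simulated with assumed normal inputs: Day 1 mean 130, SD 15; shift to Day 15 mean −6, SD 10; acute change mean −10, SD 5.

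| Column | Mean | SD |
|---|---|---|
| Day 15 post − Day 1 pre (planned) | −15.16 | 14.6 |
| Day 15 pre − Day 1 pre (planned) | −5.84 | 11.7 |
| Day 15 post − Day 15 pre (not planned) | −9.32 | 2.96 |

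Means subtract: −15.16 − (−5.84) = −9.32, provided the same subjects contribute to both rows. SDs do not subtract, and neither do minima and maxima. Medians do not in general, although they happened to in this simulated set.

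**3. Size for systolic pressure.** Assume reading = visit effect (SD v) + within-session noise (SD e), with v = 5 to 12 and e = 5 to 8 mmHg. These SDs are assumptions; the documents give none.

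- Variance of change from Day 1 pre-dose: 2v² + 2e²
- Variance of change from Day 15 pre-dose: 2e²
- Proportional reduction: v² / (v² + e²)
- SE of a three-subject mean: √(variance / 3)

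| v, e | SE, Day 1 reference | SE, same-day reference | Variance reduction |
|---|---|---|---|
| 5, 8 | √(178/3) = 7.7 | √(128/3) = 6.5 | 25/89 = 28% |
| 5, 5 | √(100/3) = 5.8 | √(50/3) = 4.1 | 25/50 = 50% |
| 12, 8 | √(416/3) = 11.8 | √(128/3) = 6.5 | 144/208 = 69% |
| 12, 5 | √(338/3) = 10.6 | √(50/3) = 4.1 | 144/169 = 85% |

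These are the four corners of the assumed ranges, so the reduction runs from 28% to 85%.

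**4. Sensitivity to the model.** With equal variance σ² at each time, the SD of a change is σ√(2(1 − ρ)). For an assumed two-week ρ of 0.4 to 0.8 this is 1.10σ to 0.63σ. For an assumed within-visit ρ of 0.80 to 0.95 it is 0.63σ to 0.32σ. The planned change is then 1.0 to 3.5 times as variable. At ρ = 0.80 for both there is no gain in precision. The mixing in step 1 does not depend on any of these values.

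Steps 3 and 4 concern vital signs. The Day 16 labs and their proposed reference come from different days, so a within-session model does not fit them.

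**The case against.** **No inference depends on this.** Sample size rests on feasibility, SAP 8.5 states that there are no formal cohort comparisons, and the summaries are descriptive. The SE of a three-subject mean drives no decision. This stands and limits the weight of the point.

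**The comparison is largely visible already.** Day 15 pre-dose labs sit in the row above Day 16, and Day 15 pre-dose vital signs fall under the SAP's post-baseline time points. All subject data are listed (Listings 17 to 19 and 21), so with three subjects per cohort each acute change can be worked out. A reader might infer that the second-dose effect is lost; it is not. What is missing is its prespecified summary.

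**Acute reactions are caught elsewhere.** The protocol has at least 60 minutes of observation after dosing, DLT criteria, allergic-reaction grading that includes hypotension, recording of clinically significant abnormalities as adverse events, and DSMC review. None of these is defined by the change column. A reader might also suppose that the second exposure is where sensitisation would show; the documents do not say so.

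**The Day 1 reference is legitimate.** Change from baseline in labs is a primary safety endpoint (Protocol 4.1.1, whose list of days does not include Day 16), and the two-week component may carry a real first-dose effect. Replacing the reference would remove the cumulative change from those rows. This stands, and it is why the remedy is an added column.

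**The immediate reading may still appear.** A reader might infer from the shell that it is left out of the tables. The shell draws only heart rate and Day 1 rows, and its programmer note tells the programmer to repeat it for all available times. The documents support only that the SAP does not name the reading.

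**Conclusion.** The point holds as a minor one. It is certain from the text that the change columns for Day 15 post-dose vital signs and Day 16 labs combine the acute second-dose change with the preceding 11 to 17 days, and that no SD, median or range of the acute change is planned.

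For systolic pressure the variance of the change falls by 28% to 85% with a same-day reference, if the assumed SDs are right. A reader might infer that the variance is at least halved, but that needs visit-to-visit SD to be no smaller than within-session SD, and nothing in the documents establishes this. No such figure is offered for labs.

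The SAP's silence on the immediate post-dose reading, and the placing of the timed Day 15 readings in Protocol 6.2.4, are gaps in wording that should be closed. No test, sample size or error rate changes.

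**What to change.** 1. In SAP 10.5 and Table 19, keep change from baseline and add change from the Day 15 pre-dose value for the Day 15 post-dose vital signs, with N, mean, SD, median, minimum and maximum.
2. In SAP 10.3 and Tables 16.1 to 16.3, do the same for Day 16, with the Day 15 pre-dose value as the added reference.
3. Name the immediate post-dose reading in SAP 10.5 and draw its row in Table 19, so that it does not rest on a catch-all note.
4. Reconcile the two vital-sign entries in Protocol 6.2.4 with each other and with Table 4-1, and make the Day 15 rows of Table 19 follow the result.

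The cost is a few sentences and some extra table rows. The protocol already schedules the readings, so no new data collection is needed.
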